Treatment of fungal toenail infection requires an understanding of the ultrastructure of the nail. Keratinocytes exist within the nail plate and are strongly linked by numerous desmosomes and phospholipid layers. The nail plate consists of 3 different layers: a thin ventral plate, a thick intermediate plate, and a thin dorsal plate (Figure 1). The cells of the dorsal plate are very flat and lack nuclei. The cells of the intermediate plate are less flat and have cytoplasmic portions. The ventral plate consists of 1-2 cell layers with nuclear residues. As a result of their composition and structure, the 3 nail plate layers can have different penetration characteristics for a medicinal product.

A Randomized, Placebo-Controlled, Double-Blind, Parallel-Group, Multi-Site Phase 2b Clinical Study to Assess the Efficacy, Safety and Tolerability of 8-Week Regimens of Novexatin®, 10% Topical Solution (Taro Pharmaceuticals, USA, Inc.) in Patients with Mild to Moderate Onychomycosis

Figure 1: Anatomy of the Nail

At present, the currently approved, marketed medicinal products available for the treatment of fungal nail infection have a number of shortcomings in regard to both safety and efficacy.^{2,6-8} The topical therapies (ciclopirox and amorolfine) have poor levels of efficacy.⁹ The systemic treatment options (terbinafine and itraconazole especially) have associated adverse effects and toxicity profiles of concern.^{10,11} Several authors reported liver toxicity and therefore monitoring of liver function during itraconazole therapy is important.¹¹ This unmet clinical need and a detailed understanding of host-pathogen interactions and the microbiology of fungal toenail infection have led to the development of Novexatin® by NovaBiotics. Novexatin is a backbone cyclized peptide of 7 L-isomer arginine residues; the chemical name is cyclo[arginyl- arginyl - arginyl - arginyl - arginyl - arginyl - arginyl], acetate. The L-isomer component comprises 93% of the Cyclo[7xArg] material with 7% as a single amino acid in the D-configuration.¹² This third-generation, cationic antimicrobial peptide (cAMP) provides the active component of a treatment for topical administration for fungal infection of the nail. Novexatin has the potential to address the significant efficacy and safety shortcomings of the limited number of current and emerging treatment options of onychomycosis.

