18. Use within 4 weeks before baseline of 1) topical antifungal therapies on the feet, 2) immunomodulators or 3) systemic corticosteroids.
19. Use of topical corticosteroids on the feet within 2 weeks before baseline.
20. Use of systemic antifungal agents for the treatment of onychomycosis or any antifungal with known activity against dermatophytes within the previous 24 weeks.
21. Current evidence of drug abuse or history of drug abuse within 1 year before the first dose, including, in the opinion of the Investigator, history of alcohol abuse or active alcoholism.
22. Inability to understand the protocol requirements, instructions, and study-related restrictions, the nature, scope, and possible consequences of the clinical study.
23. Unlikely to comply with the protocol requirements, instructions, and study-related restrictions, such as uncooperative attitude, inability to return for follow-up visits, and improbability of completing the clinical study.
24. Patient is the Investigator or his/her deputies, research assistant, pharmacist, clinical study coordinator, other staff or relative thereof directly involved in the conduct of the clinical study or employed by the clinical site, or a first-degree relative of a site employee.
25. Patients with previous exposure to the study drug, or with known allergy to the drug or any of its components.

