9.3.3 Restrictions during the Study

The following concomitant medications will not be allowed during the study and during the specified washout periods before Visit 1:

Restricted medication	Examples (not comprehensive)	Washout
Systemic antifungals	Sporanox®,	24 weeks

A Randomized, Placebo-Controlled, Double-Blind, Parallel-Group, Multi-Site Phase 2b Clinical Study to Assess the Efficacy, Safety and Tolerability of 8-Week Regimens of Novexatin®, 10% Topical Solution (Taro Pharmaceuticals, USA, Inc.) in Patients with Mild to Moderate Onychomycosis

	terbinafine,	
Topical antifungals on feet	Lotrimin®, tea tree oil, crystal violet	4 weeks
Systemic corticosteroids	prednisone, prednisolone	4 weeks
Topical corticosteroids		2 weeks
Immunomodulators	chemotherapy, rheumatoid arthritis drugs	4 weeks

Note: Treatment for tinea pedis or tinea cruris will be allowed during the study, and a topical antifungal medication will be provided to patients as deemed necessary by Investigator.

Occasional short term use of systemic and topical corticosteroids other than the feet is allowed to the extent that, in the opinion of the investigator, does not compromise the study results.

The use of topical corticosteroids on the feet is restricted for the entire study.

The use of intranasal, inhaled or ophthalmic corticosteroids is allowed up to 1 mg/day.

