9.3.5 Early Terminations and Protocol Deviations

The following rules and conventions will be used for patients who terminate from the study early or are dropped from the study because of protocol deviations.

If a patient terminates from the study early, all efforts will be made to complete Visit 7 study procedures.

Any patient who either requests to be dropped from the study because of lack of therapeutic efficacy or is dropped by the Investigator for lack of therapeutic efficacy will automatically be considered a "clinical failure" irrelevant of their target toenail assessment score at the termination visit.

Any patient who uses any protocol restricted medication specifically for the treatment of their infection will be discontinued from further participation in the study and automatically be considered a "clinical failure" irrelevant of their target toenail assessment score at the last visit.

Any patient who uses any protocol restricted medication NOT specifically for the treatment of their onychomycosis will be discontinued from further participation in the study. The patient will be considered a "clinical cure" or "clinical failure" based on the target toenail assessments at the termination visit.

Any patient who is dropped for any other reason, other than those covered above, had a positive baseline culture and makes at least one post-baseline visit where clinical assessments for target toenail are performed and/or a KOH and/or mycological culture result is obtained, will be

A Randomized, Placebo-Controlled, Double-Blind, Parallel-Group, Multi-Site Phase 2b Clinical Study to Assess the Efficacy, Safety and Tolerability of 8-Week Regimens of Novexatin[®], 10% Topical Solution (Taro Pharmaceuticals, USA, Inc.) in Patients with Mild to Moderate Onychomycosis

included in the ITT. Examples would include: failure to use the study products as required by the protocol (see section 9.4.5), patient withdraws consent for continued participation, patient fails to make study visits on a timely basis.

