**Figure 1 Study Schematic**

| PROCEDURE   | Visit 1   | Visit 2  | Visit 3                              | Visit 4              | Visit 5                                      | Visit 6                              | Visit 7                                   |
|---|-----------|--|--------------------------------------|----------------------|--|--------------------------------------|---|
|   | Screening | Randomization / Baseline / 1 st treatment start | 1 st treatment completion | Interim Test of cure | 2 nd treatment start Test of cure | 2 nd treatment completion | 4 weeks post-treatment Test of cure or ET |
| Day   | -35 to -1 | 1  | 57 ± 4 (Week 8)                      | 141 ± 7 (Week 20)    | 281 ± 14 (Week 40)                           | 337 ± 14 (Week 48)                   | 365 ± 14 (Week 52)                        |
| Informed Consent  | X         |  |                                      |                      |  |                                      |   |
| Inclusion/ Exclusion Criteria Review  | X         | X  |                                      |                      |  |                                      |   |
| Demographics  | X         |  |                                      |                      |  |                                      |   |
| Medical History   | X         |  |                                      |                      |  |                                      |   |
| Physical Examination  | X         |  |                                      |                      |  |                                      | X   |
| Vital Signs   | X         |  | X                                    |                      | X  | X                                    | X   |
| KOH test  | X         |  |                                      | X                    |  |                                      | X   |
| Fungal Culture collection   | X         |  |                                      | X                    |  |                                      | X   |
| Clinical Lab Tests  | X         |  | X                                    |                      |  |                                      | X   |
| Target Nail trimming (if needed) before nail involvement/appearance assessments |           | X  | X                                    | X                    | X  | X                                    | X   |

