Statistical testing will begin with comparison 1. If statistical significance is attained with comparison 1 ( $p < 0.05$ ), then a claim of superiority for comparison 1 can be made and the next comparison in the hierarchical evaluation scheme can be tested for statistical significance. If statistical significance is not attained for comparison 1 ( $p \geq 0.05$ ), then testing of all subsequent comparisons is stopped. The hierarchical, conditional-stepwise evaluation scheme allows for each comparison to be evaluated at the 5% level, while preserving an overall type I error rate of no more than 5%. For the proportion of patients in each treatment group with a complete and almost complete therapeutic cure, complete and satisfactory clinical cure and mycological cure of onychomycosis of the target toenail, the statistical analysis for superiority will be conducted using a two-sided Cochran-Mantel-Haenszel (CMH) exact test, stratified by clinical site, at the 5% significance level. The primary and secondary analyses will be performed using an observed case (OC) analysis in the ITT population. Patients discontinued because of lack of treatment effect will be included in the primary analysis as treatment failures.

The following two sensitivity analyses will also be performed on the primary efficacy endpoint in the hierarchical, conditional-stepwise evaluation scheme:

**NOVUM PHARMACEUTICAL RESEARCH SERVICES  
STATISTICAL ANALYSIS PLAN**

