**8.5 Methods for Handling Missing Data**

For demographic and baseline characteristics, each variable will be analyzed using all available data. Patients with missing data will be excluded only from analyses for which data are not available.

The following rules and conventions will be used for patients who terminate from the study early or are dropped from the study because of protocol deviations.

Any patient who either requests to be dropped from the study because of lack of therapeutic efficacy or is dropped by the Investigator for lack of therapeutic efficacy will automatically be considered a "clinical failure" regardless of their target toenail assessment score at the termination visit.

Any patient who uses any protocol restricted medication specifically for the treatment of their infection will be discontinued from further participation in the study and automatically be considered a "clinical failure" regardless of their target toenail assessment score at the last visit.

Any patient who uses any protocol restricted medication NOT specifically for the treatment of their onychomycosis will be discontinued from further participation in the study. The patient will be considered a "clinical cure" or "clinical failure" based on the target toenail assessments at the termination visit.

Any patient who is dropped for any reason other than those covered above will be included in the ITT, provided they had a positive baseline culture and applied at least one dose of the study product. Examples would include: failure to use the study products as required by the protocol, patient withdraws consent for continued participation, patient fails to make study visits on a timely basis.

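### A patient who takes a systemic antifungal for a reason other than the nail infection can still be scored as a cure at a test-of-cure visit

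*SAP*

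**What the plan says.** Two rules in SAP 8.5, carried over from protocol 9.3.5, cover restricted medication. They divide patients by the reason for use.

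- Taken for the infection: "Any patient who uses any protocol restricted medication specifically for the treatment of their infection will be discontinued from further participation in the study", and the patient is automatically a clinical failure whatever the nail shows.
- Taken for something else: "Any patient who uses any protocol restricted medication NOT specifically for the treatment of their onychomycosis will be discontinued from further participation". The nail then decides: "The patient will be considered a 'clinical cure' or 'clinical failure' based on the target toenail assessments at the termination visit".

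The restricted drugs are listed in protocol 9.3.3, which opens: "The following concomitant medications will not be allowed during the study and during the specified washout periods before Visit 1". Systemic antifungals are the first entry, with Sporanox and terbinafine as examples and a 24-week washout. A note allows treatment of tinea pedis or tinea cruris and provides a topical antifungal for it.

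Elsewhere the protocol treats these drugs as active against the disease under study. Section 7.2 says: "The systemic treatment options (terbinafine and itraconazole especially) have associated adverse effects and toxicity profiles of concern". Exclusion 20 bars "Use of systemic antifungal agents for the treatment of onychomycosis or any antifungal with known activity against dermatophytes within the previous 24 weeks".

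On analysis, SAP 8.2.1 says: "The primary and secondary analyses will be performed using an observed case (OC) analysis in the ITT population". Its two sensitivity analyses add only patients with no assessment in the Day 365 ± 14 or Day 141 ± 7 window.

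**The concern.** Whether a systemic antifungal clears the nail does not depend on why it was prescribed. Exclusion 20 accepts this at entry, where known activity against dermatophytes is enough to exclude. After randomization only the indication counts, so the same exposure can end in a recorded cure.

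The first objective is the cure rate of the study product under each regimen. A cure after a course of terbinafine for another condition says little about that rate. Secondary endpoints 3 and 4 need only the nail reading. The primary endpoint also needs negative KOH and culture, but a drug active against dermatophytes could turn those negative as well, so mycology is not an independent safeguard.

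**Working it through.** **1. Can a user's reading enter an analysis?**

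- A user is discontinued, and the site tries to complete Visit 7 procedures, which include the nail assessment, KOH and culture (protocol 9.3.5 and 9.5.7).
- Diaries are reviewed for concomitant medication at Visits 4, 5 and 7 (protocol 9.5.4, 9.5.5, 9.5.7). These are the test-of-cure visits, so use discovered there comes with an in-window reading.
- An in-window reading is an observed case. It is not missing, so neither sensitivity analysis re-scores it.
- SAP 8.2.1 names only discontinuation for lack of effect as failure in the primary analysis, which does not apply here.

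So the route to a scored cure exists, but only for in-window readings.

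**2. The plan's own sample size.** Inputs from protocol 10.2 and SAP 5: 49% versus 21%, two-sided 0.05, pooled Z test, 23% dropout.

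n = [1.960·√(2 × 0.35 × 0.65) + 0.842·√(0.49 × 0.51 + 0.21 × 0.79)]² / 0.28² = (1.322 + 0.543)² / 0.0784 ≈ 44.4, so 45 per group. The plan uses 46. Power at 46 is 81.5% by normal approximation and 81.6% by exact enumeration. 46 / 0.77 = 59.7, so 60 per group and 180 in total. The plan's figures reproduce.

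**3. Size of the effect, B versus C at Day 365.** Assumptions not in the documents: k users among 46 in every arm, k from 0 to 4; a share c of users read as cured; every user's reading counted at Day 365; users who read as clinically cured also mycologically cured.

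Cures in an arm = Binomial(k, c) + Binomial(46 − k, p), with p = 0.49 or 0.21. Setting c = 0 gives the failure rule. Power is the exact probability that the two-sided pooled Z test rejects. Leaving users out means 46 − k per arm.

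| k per arm | As written, all users cured | Users are failures | Gain, all cured | Gain, 10% cured | Users left out | Failure rule below left out |
|---|---|---|---|---|---|---|
| 0 | 81.6% | 81.6% | 0 | 0 | 81.6% | 0 |
| 1 | 79.3% | 80.5% | 1.2 | 0.2 | 81.6% | 1.1 |
| 2 | 76.9% | 79.4% | 2.5 | 0.5 | 81.2% | 1.8 |
| 3 | 74.3% | 78.2% | 3.9 | 0.7 | 80.2% | 2.0 |
| 4 | 71.7% | 76.9% | 5.2 | 1.0 | 78.9% | 2.0 |

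Gains and losses are in percentage points.

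**4. Type I error, equal use.** With p = 0.21 in both arms, two-sided rejection is 5.0% at k = 0. For k = 1 to 4 with all users cured it is 4.0%, 3.2%, 2.7% and 2.2%, because identical fixed cures in both arms dilute the comparison.

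**5. Unequal use, illustration only.** The same formula with three users, all cured and all in Group C, gives power of 62.3% as written. If all three are in Group B and there is no true effect, the chance of a false win for B rises from 2.5% to 7.3%. The direction depends on which arm the users fall in.

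The SAP has replaced the Z test with an exact CMH test stratified by site. Site sizes are not given, so that power cannot be computed. The figures above use the sizing test.

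**The case against.** The strongest reply is that the plan already deals with most such patients. They are discontinued, the analyses are observed-case at fixed visits, and sensitivity analysis 1 scores a patient with no in-window assessment as a failure on the primary endpoint. This stands, and it is why the point is confined to in-window readings.

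A reader might go further and infer that any termination reading, whenever taken, is used at Day 365, because the Visit 7 column is headed "4 weeks post-treatment Test of cure or ET" and SAP 8.5 states no window. The documents do not support that as the intended analysis: SAP 8.2.1 treats patients without a Day 365 ± 14 assessment as missing. Saying how termination readings relate to the windows would be a useful clarification, but it concerns all early terminations and is separate from this point.

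A reader might also infer that the rule biases the trial toward the active product. It is prespecified, identical in all arms and applied under blinding. The documents give no reason to expect more use in one arm, and equal use does not raise type I error. The unequal cases in step 5 show sensitivity to chance imbalance, not an expected bias.

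Two further replies have some force. Exclusion 20 is an entry rule and does not dictate outcome scoring; it shows only that the protocol regards activity, not just indication, as relevant. And failure whatever the indication is a choice of estimand: if the alternative is to leave users out, it lowers power by about 1.1 to 2.0 points. Neither reply justifies recording as a study-product cure a nail that another antifungal may have cleared.

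**Conclusion.** The point holds and is minor. As written, a patient who takes a systemic antifungal active against dermatophytes for a non-nail reason, and whose termination reading falls in a test-of-cure window, can be a clinical cure. The patient is also a complete therapeutic cure if KOH and culture are negative. No other provision re-scores that patient.

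The size rests on an unknown number of users. With none, nothing changes. With 1 to 4 of 46 in every arm, scoring them as failures gains 1.2 to 5.2 points of power for B versus C if all read as cured. That is an upper bound, since it also assumes that every reading counts at Day 365. At 10% cured the gain is about 0.2 to 1.0 points. The documents give no expected rates for endpoints 3 and 4, so no figure is offered for them.

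The point does not extend to the topical treatment of tinea that protocol 9.3.3 allows.

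**What to change.** Add one sentence to SAP 8.5 and to protocol 9.3.5: a patient who used a systemic antifungal active against dermatophytes before a test-of-cure visit is a failure at that visit and at later test-of-cure visits, whatever the indication, including systemic treatment of tinea. Keep the nail-reading rule for other restricted drugs, such as corticosteroids and immunomodulators, and leave the permitted topical tinea treatment untouched.

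No new data are needed. Listing L16.2.4.3 already carries medication, route, dates and indication. SAP 8.7 already records a change to 8.5 and can record this one.

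The costs are small but real. A few genuine cures will count as failures. Compared with leaving users out, B versus C loses about 1.1 to 2.0 points of power for 1 to 4 users per arm. Use mainly in placebo would favour active treatment: with three users in Group C only, power under the failure rule is 85.8% against the 81.6% base. These patients would also become observed failures, so sensitivity analysis 2 would no longer count a Group C user as a success; the SAP should say so.

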**8.6 Interim Analyses**

There is no interim analysis planned in this study.

**NOVUM PHARMACEUTICAL RESEARCH SERVICES  
STATISTICAL ANALYSIS PLAN**

Novexatin 10% topical solution

Protocol / Study No. NVXT 1404/71442603

**8.7 Changes to the Protocol Defined Statistical Analysis Plan**

The protocol states that the statistical analysis for superiority will be conducted using two-sided Z-Tests and a pooled response rate for the standard error of the difference in proportions for each comparison of interest. The CMH exact test stratified by clinical site is preferred for a multi-site study for which the randomization is intended to be balanced among treatments within each site (i.e., stratified by site), because it accounts for the variability in clinical site whereas the Z-test does not account for site variability in the model. During the analysis, the statistical analysis for superiority will be conducted using a two-sided Cochran-Mantel-Haenszel (CMH) exact test, stratified by clinical site, at the 5% significance level.

The wording in section 8.5 “Methods for Handling Missing Data” was updated to coincide with the ITT definition. The ITT states that patients will be included in the ITT as long as they have received one dose of assigned study product and had a positive mycological culture at Visit 1.

Additional analyses that were not delineated in the protocol were included in section 8.2.3 of the SAP.

**9. TABLE, LISTING AND FIGURE SHELLS**

The following shells provide a framework for the display of data from this study. These shells may not be reflective of every aspect of this study but are intended to show the general layout of the Tables, Listings and Figures that will be included in the final clinical study report. Tables, Listings and Figures are numbered following the ICH structure. Table headers, variables names and footnotes will be modified as needed following data analyses. All descriptive and inferential statistical analyses will be performed using SAS® statistical software Version 9.4 or higher, unless otherwise noted.

